10.3.2.3. Concomitant Therapy

Previous and concomitant medications will be summarized and will be presented by WHO Anatomic Therapeutic Class Level 4 and WHO preferred term. Concomitant DMARDs, concomitant corticosteroids, and concomitant NSAIDs will also be summarized. Treatment group comparisons in Period 2 will be conducted using Fisher's exact test.

10.3.2.4. Treatment Compliance

Treatment compliance with investigational product will be summarized. A patient will be considered overall compliant for each study period if he/she is missing no more than 20% of the expected doses, does not miss 2 consecutive doses, and does not over-dose (i.e., take more injections at the same time point than specified in the protocol).

Proportions of patients compliant by visit and overall will be compared between treatment groups during Period 2 using Fisher's exact test.

10.3.3. Efficacy Analyses

10.3.3.1. Primary Analyses

The primary analysis, the proportion of patients in the combined ixekizumab treatment group who do not experience a flare during Period 2 compared with placebo, will be based on the Randomized Withdrawal ITT Population.

Treatment comparison between combined ixekizumab treatment group and placebo in the proportion of patients who do not experience a flare during Period 2 will be analyzed using the logistic regression model defined in Section 10.3.1.2. Missing data will be imputed using the NRI method described in Section 10.3.1.5.1.

10.3.3.2. Major Secondary Analyses

The major secondary analysis for the time to flare will be based on the Randomized Withdrawal ITT Population. Time to flare will be calculated in weeks as follows:

$$\frac{\text{Date of flare} - \text{Date of First Dose in Period 2} + 1}{7}$$

The date of flare is the time point when the patient qualifies for retreatment. If the date of the first dose is missing, the date of randomization will be used. Patients who complete Period 2 without a flare will be censored at the date of completion (i.e., the date of the last scheduled visit in the period). Patients without a date of completion or discontinuation for Period 2 and who did not experience a flare will be censored at the latest nonmissing date out of the following dates: date of last dose and date of last attended visit in Period 2 (scheduled or unscheduled).

Treatment comparisons between ixekizumab and placebo in time to flare for the Randomized Withdrawal ITT Population will be analyzed using a stratified log-rank test with treatment, geographic region, and originating study in the model. The Kaplan-Meier product limit method

will be used to estimate the survival curves for time to flare. Time to flare will also be summarized graphically by treatment group using Kaplan-Meier techniques.

Treatment comparisons in the proportion of patients who do not experience a flare at Week 64 (Group A: Visit 10/Group B: Visit 515) will be analyzed using the logistic regression model defined in Section 10.3.1.2. Missing data will be imputed using NRI method described in Section 10.3.1.5.1.

The 2-year radiographic progression reflected by change from baseline of originating studies RHBV and RHBW to Week 56 of Study RHBY (Group A: Visit 9/Group B: Visit 513) will be measured by mSASSS score and summarized by treatment. The comparison of the ixekizumab treatment group to the historical control will be analyzed by ANCOVA, with baseline score as covariate. The historical control will be defined in the SAP. Within-treatment changes from baseline along with 95% CI will be assessed by a paired t-test using the LS means.

10.3.3.3. Other Secondary Efficacy Analyses

There will be no adjustment for multiple comparisons. Analyses will be conducted for the other secondary objectives defined in Section 4.

The secondary efficacy and health outcomes analysis for Period 2 will be based on the Randomized Withdrawal ITT Population or the Flare Population. Additional efficacy and health outcome analysis for combined Periods 1, 2, and 3 analyses will be based on the Long-Term Ixekizumab Treatment Efficacy Population.

10.3.3.3.1. Combined Periods 1, 2, and 3

The long-term treatment effect in both categorical and continuous variables will be summarized by treatment group at each scheduled visit including Week 24, Week 64, and Week 104. Missing data will be imputed using mNRI for categorical efficacy variables, described in Section 10.3.1.5.2, and mBOCF and multiple imputation for continuous efficacy variables, described in Sections 10.3.1.5.3 and 10.3.1.5.4, respectively.

10.3.3.3.2. Period 2 (Extension Period, Including Blinded, Randomized Withdrawal–Retreatment)

The other secondary analysis during Period 2 will be based on the Randomized Withdrawal ITT and Flare Populations.

For the Randomized Withdrawal ITT Population, all categorical efficacy variables and treatment group comparisons will be analyzed at each visit using the logistic regression model described in Section 10.3.1.2.1. Missing data will be imputed using the NRI method described in Section 10.3.1.5.1. All continuous efficacy variables and treatment group comparisons will be analyzed at each visit using the ANCOVA models as described in Section 10.3.1.2.1 when appropriate. For the ANCOVA analysis, missing data will be imputed by the mBOCF as described in Section 10.3.1.5.3.

For the Flare Population who were retreated with ixekizumab following the flare, the following summaries will be provided:

- The proportion of patients who regain sustained remission criteria within 16 weeks after ixekizumab retreatment will be summarized by the original re-randomization treatment group.
- The proportion of patients with ASAS20 as well as the proportion of patients with ASAS40 within 16 weeks after ixekizumab retreatment will be summarized by the original re-randomization treatment group.

CCI

10.3.4. Safety Analyses

Safety will be assessed by summarizing and analyzing AEs including adjudicated cerebrocardiovascular events, IBD events, laboratory analytes including neutrophil counts, QIDS-SR16, C-SSRS, and vital signs. The duration of treatment exposure will also be summarized.

Primary safety analyses will be based on the Randomized Withdrawal Safety Population in Period 2.

For combined Periods 1, 2, and 3, safety data will be summarized for the Lead-In Period Safety Population.

For Period 2, safety data will be summarized for the Randomized Withdrawal Safety Population. Treatment group comparisons will be performed on categorical safety data using Fisher's exact test as described in Section 10.3.1.2.1; continuous safety data will be analyzed by an ANCOVA model.

For Period 4 safety data will be summarized according to the treatment patients were on prior to entering Period 4.

The categorical safety measures will be summarized with incidence rates. The mean change of the continuous safety measures will be summarized by visits.

Further details will be described in the SAP.

10.3.5. Pharmacokinetic/Pharmacodynamic Analyses

Blood samples for determination of ixekizumab concentrations will be collected and may be analyzed using graphical methods to aid in interpretation of the immunogenicity data.

Additional exploratory analyses of the data may be conducted if deemed appropriate.

10.3.6. Other Analyses

10.3.6.1. Health Outcomes

There will be no adjustment for multiple comparisons. Analyses will be conducted for the other secondary health outcomes objectives as defined in Section 4.

Period 2 (Extension Period, Including Blinded, Randomized Withdrawal–Retreatment):

Unless otherwise specified, the other secondary analyses during Period 2 will be based on the Randomized Withdrawal ITT Population.

Treatment comparisons in the proportion of patients achieving a categorical response at specified time points will be analyzed using the logistic regression model defined in Section 10.3.1.2.1. Missing data will be imputed using the NRI method described in Section 10.3.1.5.1.

For all continuous health outcomes variables, treatment group comparisons will be analyzed using the ANCOVA model defined in Section 10.3.1.2.1; missing data will be imputed by the mBOCF method as described in Section 10.3.1.5.3.

Combined Periods 1, 2, and 3:

Data collected in combined Periods 1, 2, and 3 will be summarized for the Long-Term Ixekizumab Treatment Efficacy Population. The within-treatment group comparisons may be conducted as appropriate.

10.3.6.2. Subgroup Analyses

Subgroup analyses will be conducted for time to flare and the proportion of patients who experienced a flare for the Randomized Withdrawal ITT Population.

Subgroup analyses may be conducted based on gender, age category, race, geographic region, population (radiographic and nonradiographic axSpA), origination study, and CRP status at the time of randomization in Period 2. Additional subgroups may be described in the SAP.

The Kaplan-Meier product limit method will be used to estimate the survival curves or time to flare. Analyses will be performed using a log-rank test with treatment, subgroup, and the interaction of treatment-by-subgroup included as factors in the model.

For the proportion of patients who experience a flare, a logistic regression model will be used with treatment, subgroup, and the interaction of treatment-by-subgroup included as factors. Missing data will be imputed using NRI.

The subgroup-by-treatment interaction will be tested at the significance level of 0.10. Treatment group differences will be evaluated within each category of the subgroup, regardless of whether the interaction is statistically significant.

Detailed description of the subgroup variables will be provided in the SAP. Additional subgroup analyses on efficacy or subgroup analyses on safety may be performed as deemed appropriate and necessary.

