## 6.14. Subgroup Analyses

### 6.14.1. Efficacy Subgroup Analyses

Unless otherwise specified, subgroup analysis will be conducted for Long-Term Ixekizumab Efficacy Population, RW ITT Population and Ixekizumab Structure Population for selected outcomes.

For the RW ITT Population during Period 2 to compare the Combined Ixekizumab group to the placebo group on proportion of patients who do not experience a flare, a logistic regression analysis, including variables of treatment, subgroup, and treatment-by-subgroup interaction, will be used. The treatment-by-subgroup interaction will be tested at the 10% significance level. If any group within the subgroup is <10% of the total population, only descriptive statistics will be provided for that subgroup (that is, no inferential testing).

The following subgroups will be analyzed for the Long-Term Ixekizumab Efficacy Population on ASAS40 and change from baseline in BASDAI at Week 64 in RHBY, unless otherwise specified. All subgroups are based on records at Week 0 in originating studies. Descriptive statistics will be provided for the observed cases.

- Patient Demographics Subgroups:
  - Sex;
  - Age category: <40 years,  $\geq$ 40 years;
  - Age category: <50 years,  $\geq$ 50 years;
  - Weight: <70 kg,  $\geq$ 70 kg;
  - BMI: underweight ( $<18.5 \text{ kg/m}^2$ ); normal ( $\geq 18.5$  and  $<25 \text{ kg/m}^2$ ); overweight ( $\geq 25$  and  $<30 \text{ kg/m}^2$ ); obese ( $\geq 30$  and  $<40 \text{ kg/m}^2$ ); or extreme obese ( $\geq 40 \text{ kg/m}^2$ );
  - Ethnicity: Hispanic/Latino, Non-Hispanic/Non-Latino;
  - Race: American Indian/Alaska Native, Asian, Black/African American, Native Hawaiian or other Pacific Islander, White, or Multiple.

- Geographic Region and Study Subgroups:
  - Geographic region: Europe or Non-Europe;
  - Geographic region: US (including Puerto Rico sites if any) or Non-US;
  - Originating Study: RHBV, RHBW or RHBX;
  - Originating Study: r-axSpA (RHBV and RHBW) vs nr-axSpA (RHBX).
- Other Patient Characteristics Subgroups:
  - Baseline CRP categories:
    - $\leq 5.00 \text{ mg/L}$  or  $> 5.00 \text{ mg/L}$ ;
    - $\leq 10.00 \text{ mg/L}$  or  $> 10.00 \text{ mg/L}$ ;
  - Duration of symptom of onset category:  $< 5 \text{ years}$  or  $\geq 5 \text{ years}$ ;
  - Duration of symptom of onset category:  $< 10 \text{ years}$  or  $\geq 10 \text{ years}$ ;
  - HLA-B27 status: positive or negative;
  - Smoking status: current or former/never;

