  - Concomitant conventional disease-modifying antirheumatic drug (cDMARDs) (methotrexate, sulfasalazine, hydroxychloroquine) at baseline: yes or no;
  - History of arthritis/ dactylitis (peripheral): yes (historical /current) or no;
  - History of uveitis/ inflammatory bowel disease / psoriasis (extra-axial): yes or no;
  - History of enthesitis: yes or no.

The following subgroups will be analyzed for the RW ITT Population on proportion of patients who do not experience a flare in Period 2:

- Originating Study: RHBV, RHBW, RHBX;
- Originating Study: r-axSpA (RHBV, RHBW) vs. nr-axSpA (RHBX);
- TNFi experience: bDMARD-naïve (RHBV and RHBX) vs. TNFi-experience (RHBW);
- Length of treatment on ixekizumab for RHBX patients: 24-44 weeks, 52-60 weeks, 76 weeks;
- Length of treatment on ixekizumab for RHBV and RHBW patients: 56-60 weeks, 76 weeks.

The following subgroups will be analyzed for the Ixekizumab Structure Population on change from baseline in mSASSS, non-progression rate and no-new-syndesmophyte, respectively:

- cDMARD Experience: Yes or No;
- Baseline NSAID Use: Yes or No;
- TNFi Experience: Yes or No;
- Sex: Female or Male;
- Smoking Status: current or former/never;
- Baseline CRP Status:  $\leq 5.00 \text{ mg/L}$  or  $> 5.00 \text{ mg/L}$ ;
- Baseline mSASSS $\geq 2$ : Yes or No;
- Baseline MRI spine SPARCC score  $\geq 2$ : Yes or No;
- Group: A or B.

Additional subgroup analyses on efficacy may be performed as exploratory analyses.

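### Protocol 10.3.6.2 promises a treatment-by-subgroup interaction test for time to flare from a log-rank test, which cannot supply one, and the readable SAP omits that analysis without saying so

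*Protocol*

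**What the plan says.** Protocol 10.3.6.2 makes a firm commitment: "Subgroup analyses will be conducted for time to flare and the proportion of patients who experienced a flare for the Randomized Withdrawal ITT Population". Only the choice of subgroup variables is left permissive. For time to flare it names Kaplan-Meier curves and then this test: "Analyses will be performed using a log-rank test with treatment, subgroup, and the interaction of treatment-by-subgroup included as factors in the model". For the flare proportion it names logistic regression with the same three terms. It then adds: "The subgroup-by-treatment interaction will be tested at the significance level of 0.10". Treatment differences are to be examined within each category whatever the interaction result. On the SAP's role it says: "Detailed description of the subgroup variables will be provided in the SAP".

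SAP 6.14.1 gives one method for this population, applied to the flare-free proportion: "a logistic regression analysis, including variables of treatment, subgroup, and treatment-by-subgroup interaction, will be used". The level follows: "The treatment-by-subgroup interaction will be tested at the 10% significance level". A subgroup variable with a level below 10% of the population gets descriptive statistics only. The list of subgroups opens: "The following subgroups will be analyzed for the RW ITT Population on proportion of patients who do not experience a flare in Period 2". Time to flare is not named there.

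Elsewhere (SAP 6.1.3.1, 6.10.2 and Table RHBY.6.5) time to flare is analysed by Kaplan-Meier and a log-rank test stratified by region and originating study. No Cox or other hazard regression appears in the readable text of either document.

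**The concern.** The protocol attaches a decision rule (interaction at 0.10) to a procedure that does not produce the statistic. The sentence reads as though the logistic-regression wording had been carried over to a rank test. A programmer following it would have to improvise, and the two nearest literal constructions do not test interaction. The SAP, where the problem could have been resolved, leaves the analysis out without comment.

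Two consequences follow. Without a valid interaction test, readers of the within-category results will compare p-values between subgroups, which does not show that the effects differ. And if the analysis is done after all, its method would be chosen at or after the Week 64 lock, when Protocol 10.3.7 has the study team unblinded.

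**Working it through.** **1. The plan's own figure.** Protocol 10.1 gives 200 patients, 2:1 allocation, flare rates of 10% and 70%, and a two-sided Fisher's exact test at 0.05. Exact enumeration for 133 versus 67 gives power above 99.99%. For the fallback of 150 (100 versus 50) it is also above 99.99%. The stated lower bounds (over 99%, over 95%) hold. No figure is stated for any subgroup test.

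**2. The two documents side by side.**

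| Subgroup outcome | Protocol 10.3.6.2 | SAP 6.14.1 (readable) |
|---|---|---|
| Flare proportion | Logistic regression with interaction: valid | Logistic regression with interaction: valid |
| Time to flare | Log-rank with interaction: not a defined test | Not listed |

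**3. Could a log-rank variant stand in?** This was checked by simulation: 1000 trials per scenario, 133 versus 67 patients, exponential time to flare, censoring at 40 weeks, a two-level subgroup with each level equally likely, all tests at 0.10. The placebo hazard is −ln(0.30)/40 per week and the planned ixekizumab hazard is −ln(0.90)/40, so the planned hazard ratio is ln(0.90)/ln(0.30) = 0.0875. The table shows how often each test rejected.

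| Truth | Log-rank stratified by subgroup | Log-rank-score test on the treatment × subgroup product | Cox interaction test |
|---|---|---|---|
| No interaction, planned effect | 100% | 100% | 9% |
| No interaction, HR 0.4 in both levels | 99.6% | 74% | 9% |
| Crossed, HR 0.4 versus 2.5 | 38% | 100% | 99.8% |

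With no interaction a valid test should reject about 10% of the time. Only the Cox test does. The stratified log-rank responds to the overall treatment effect and loses power when effects oppose each other. The product-term test rejects heavily when there is no interaction. Some Cox fits raised a convergence warning, as can happen when a cell has very few or no flares.

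**4. What the Cox test could detect.** Expected flares are 0.10 × 133 = 13.3 on ixekizumab and 0.70 × 67 = 46.9 on placebo, 60.2 in all. The documents give no subgroup split or subgroup-specific rates, so equal rates in both levels and a range of splits are assumed. The standard error of the log ratio of hazard ratios is the square root of the sum of 1/events over the four cells.

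For a 50/50 split: √(1/6.65 + 1/6.65 + 1/23.45 + 1/23.45) = 0.621. Power for a ratio R is Φ(ln R/SE − 1.645) + Φ(−ln R/SE − 1.645), which gives 17%, 30% and 55% for R = 1.5, 2 and 3. The ratio needed for 80% power is exp[(1.645 + 0.842) × 0.621] ≈ 4.7.

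| Split | SE | Power at R = 2 | R for 80% power |
|---|---|---|---|
| 50/50 | 0.621 | 30% | 4.7 |
| 30/70 | 0.678 | 27% | 5.4 |
| 10/90 | 1.036 | about 18% | 13 |

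**5. Sparse cells.** At the SAP's 10% size limit a level holds about 0.10 × 133 ≈ 13 ixekizumab patients. The chance of no flare among them is 0.9^13 ≈ 25%, in which case the hazard ratio in that level is not finite.

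**The case against.** The strongest reply is that Protocol 10.3.1 leaves full analysis detail to the SAP, that SAP 6.14.1 restricts subgroup work to selected outcomes, and that time to flare is not among them for this population. On that view the invalid test is simply not planned. This stands in part: the SAP does not repeat the faulty method. But the protocol text is current and firm, and it delegates the subgroup variables to the SAP, not the choice of endpoint. A silent omission leaves the two documents in conflict. Protocol 10.3.1 itself asks that changes below amendment level be described and justified in the study report.

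A second reply is that the wording is shorthand. Protocol 10.3.1.2.1 also describes the main log-rank test as having region and originating study in the model, and SAP 6.1.3.1 implements these as strata. That reading works for strata. It does not work for an interaction, as step 3 shows.

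Third, heterogeneity in whether patients flare is already tested validly in the same population and period, and Kaplan-Meier curves and within-category comparisons for time to flare remain feasible. This is correct and limits the loss to the time-to-flare interaction tests.

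Fourth, the exploratory sections of both documents are redacted, so a method could sit there. The statement about the SAP is therefore confined to its readable text.

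**Conclusion.** The point holds and is minor. The time-to-flare interaction test in Protocol 10.3.6.2 cannot be carried out with the procedure it names, and the readable SAP neither replaces it nor says that it has been dropped. The analysis lies outside the primary and major secondary tests and carries no multiplicity adjustment.

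Three stronger readings are not supported:
- A reader might infer that time to relapse by disease type or prior TNF inhibitor use is part of the stated rationale. Protocol 3.1 speaks only of how long withdrawn patients take to relapse. Disease type and TNF experience are described as features of the enrolled population.
- A reader might infer that about 60 flares suffice for a useful interaction test. Only about 13 are expected on ixekizumab, and even a 50/50 split gives about 30% power for a twofold ratio of hazard ratios.
- A reader might infer that the trial has no valid subgroup interaction test. It has one, for the flare-free proportion.

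The power figures rest on the protocol's flare rates, equal rates in both subgroup levels, the splits shown and the events-based variance approximation. The methodological conclusion does not depend on them.

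**What to change.** In SAP 6.14.1, and in the wording of Protocol 10.3.6.2, specify for time to flare:
- A Cox model with treatment, subgroup and treatment-by-subgroup, the interaction tested at 0.10, and hazard ratios with 95% CIs for each subgroup level.
- Stratification by region and originating study. Omit originating study as a stratum when the subgroup is originating study or a grouping of it (radiographic versus nonradiographic, TNF experience), because the subgroup term would then be constant within every stratum. Omit region when the subgroup is region.
- The SAP's existing 10% size rule, and Kaplan-Meier or other descriptive results only where any treatment-by-subgroup cell has no flares.
- A label of exploratory, with the power limits stated.

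Alternatively, state in the SAP that the time-to-flare subgroup analysis is removed, and give the reason.

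The cost is one SAP paragraph and one table, plus the matching protocol wording. The alternative costs a sentence or two. Neither needs new data.

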10.3.6.3. Immunogenicity

The analyses of anti-drug antibody (ADA) effects will be conducted on all evaluable patients within the defined Randomized Withdrawal Safety Population. Evaluable patients will be defined as either: a) patients with an evaluable baseline sample and at least 1 evaluable postbaseline sample (i.e., sample after administration of study drug); or b) patients with no evaluable baseline sample whose evaluable postbaseline samples were all ADA negative.

A treatment-emergent positive anti-drug antibody (TE-ADA+) patient will be defined as any occurrence of a greater than or equal to 4-fold or 2 dilution increase in immunogenicity titer over the baseline titer. This is equivalent to an increase in titer to $\geq 1:10$, in the case of a negative result at baseline.

The frequency and percentage (incidence) of patients with positive, negative, or inconclusive ADA at baseline and postbaseline (and NAbs at baseline and postbaseline) will be summarized by treatment group. Patients who are TE-ADA positive, TE-ADA persistent positive, and TE-ADA transient positive will also be summarized.

The potential impact of immunogenicity on efficacy responses will be evaluated, as appropriate.

Assessment of immunogenicity with respect to safety will include comparison of patients who experience treatment-emergent adverse event (TEAEs) of systemic allergy/hypersensitivity and of injection-site reactions and who also develop treatment-emergent anti-ixekizumab antibody positivity with patients who experience the same types of TEAEs but who remain treatment-emergent anti-ixekizumab antibody negative. Anti-ixekizumab antibody titers will also be evaluated in anti-ixekizumab antibody positive patients who experience these events.

